6.5.4 Pacritinib Dosage Management Guidelines for Diarrhea

Treatment with antidiarrheals is advised for all patients who experience new onset diarrhea (Table 6).

CTCAE Toxicity Grade	Management/Action		
1 or 2	No change.		
3	Hold treatment.		
	 If the toxicity resolves to grade ≤1 or to the baseline grade within 7 days, treatment may be resumed at the same level or the next lower dosage. Concomitant antidiarrheal treatment is required for patients restarting pacritinib at the 100 mg QD dosage level. 		
	• If the toxicity recurs after restart at the same dosage level, treatment may only be resumed at the next lower dosage level.		
	 If the toxicity resolves to grade ≤1 or to the baseline grade after more than 7 days, treatment may be resumed only at the next lower dosage level. Discontinuation is required if on hold from the 100 mg QD dosage level. Concomitant antidiarrheal treatment is required for patients restarting pacritinib at the 100 mg QD dosage level. 		
	 If the toxicity recurs after restart at the lower dosage level, pacritinib treatment must be discontinued. 		
4	Hold treatment.		
	 If grade 4 toxicity occurs at the lowest dosage of 100 mg QD, the patient will be discontinued from the study. 		
	 If the toxicity resolves to grade ≤1 or to the baseline grade within 7 days, treatment may be resumed, but dosage will be reduced by 1 dosage level from the level at which the toxicity was observed. Concomitant antidiarrheal treatment is required for patients restarting pacritinib at the 100 mg QD dosage level. 		

Table 6. Treatment Toxicity and Dosage Management: Diarrhea

6.5.5 Pacritinib Dosage Management Guidelines for Pacritinib-Related Nonhematologic Toxicities Other than QTc Prolongation, Decreased Cardiac Ejection Fraction, Other Cardiac Toxicities or Diarrhea

As defined in Table 7, a maximum of 2 dosage reductions are allowed for pacritinib-related nonhematologic toxicities other than QTc prolongation, decreased cardiac ejection fraction, or diarrhea.

Table 7.	Treatment Toxicity and Dosage Management: Pacritinib-Related Nonhematologic Toxicities
	Other than QTc Prolongation, Decreased Cardiac Ejection Fraction, Other Cardiac Toxicities or
	Diarrhea

CTCAE Toxicity Grade	Management/ Action
1 or 2	No change.
3	 Hold treatment.
	If the toxicity resolves to grade ≤1 or to the baseline grade within 7 days, treatment may be resumed at the same level or the next lower dosage, at the discretion of the investigator after discussion with the Sponsor.
	 Toxicity that does not resolve to grade ≤1 or to the baseline grade within 7 days requires dosage reduction to the next lower dosage.
4	 Hold treatment. If the toxicity resolves to grade ≤1 or to the baseline grade within 7 days, treatment may be resumed, but dosage will be reduced by one dosage from the level at which the toxicity was observed. If grade 4 toxicity occurs at the lowest dosage of 100 mg QD, the patient

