Patients who discontinue pacritinib treatment prior to Week 24, with or without disease progression, will continue to follow this Study Assessments Calendar through Week 24.

Patients who undergo splenic irradiation, splenectomy, or who initiate any non-protocol-directed anti-myelofibrosis treatment at any time must complete the *End of Treatment* visit within 7 days of stopping the drug and *30 Day Post End of Treatment* visit within 30 days of *End of Treatment* visit, but will not complete any additional visits.

If an arm is closed, patients randomized to that arm will end pacritinib treatment and complete the *End of Treatment* visit within 7 days of stopping the drug and *30 Day Post End of Treatment* visit within 30 days of *End of Treatment* visit.

Unscheduled visits should include physical examination, laboratory tests, and radiographic evaluations as clinically indicated in the judgement of the investigator and these results must be entered into the EDC.

Additional visits may be required for patients with baseline platelet count $\leq 50,000/\mu$ L as well as patients who have pacritinib dose modifications due to hematologic, cardiac, diarrhea, or other non-hematologic toxicities in addition to those specified in Section 6.5. Samples drawn for clinical laboratory assessments at unscheduled visits should be submitted to the central laboratory for analysis in addition to any local analysis that may be performed for the purpose of patient management. See Section 6.5 for details.

Abbreviations

Abbreviation	Full Term
AE	adverse event
ALT	alanine aminotransferase (syn: see SGPT)
ASCT	allogeneic stem cell transplantation
AST	aspartate aminotransferase (syn: see SGOT)
AUC	area under the curve
AUC _{inf}	area under the curve to infinite time
AUC _{0-t}	area of the curve up to the last measurable concentration
BAT	best available therapy
BID	twice per day
BUN	blood urea nitrogen
CBC	complete blood count
C _{max}	maximum concentration observed
C _{min}	minimum concentration observed
CRF(s)	case report form(s)
СТ	computed tomography
CTCAE	Common Terminology Criteria for Adverse Events
CYP450	cytochrome P450
DIPSS	Dynamic International Prognostic Scoring System
ECG	electrocardiogram
ECOG	Eastern Cooperative Oncology Group
eCRF	electronic case report form
EDC	electronic data capture
EPs	erythroid progenitors
ET	essential thrombocythemia
FAS	Full Analysis Set
FDA	Food and Drug Administration
FLT3	fms-like receptor tyrosine kinase 3

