2.3.2 Secondary Objectives

The secondary objectives are as follows:

- 1. To examine the dose–response relationship for efficacy, as measured by spleen volume reduction (SVR) using MRI (preferred) or CT and TSS using the Myeloproliferative Neoplasm Symptom Assessment Form Total Symptom Score version 2.0 (MPN-SAF TSS 2.0)
- 2. To examine the dose-response relationship for safety with a focus on AEs of interest
- 3. To further characterize the pharmacokinetics (PK) and pharmacodynamics (PD) of pacritinib

3 Study Design

This is a dose-finding study in patients with PMF, PPV-MF, and PET-MF (DIPSS risk score of Intermediate-1 to High-Risk), who were previously treated with ruxolitinib. The study is designed to support a pacritinib dosage selection decision. Three dosages will be evaluated, with patients randomized 1:1:1 to pacritinib 100 mg OD, pacritinib 100 mg BID, or pacritinib 200 mg BID. Randomization will be stratified by baseline platelet count ($\leq 50,000/\mu$ L; >50,000/ μ L and $\leq 100,000/\mu$ L; and >100,000/ μ L). The most recent platelet count obtained prior to start of treatment will be the basis of stratification by baseline platelet count. Assigned treatment will continue until the patient experiences progressive disease, intolerable AEs, or withdraws consent, or until the assigned treatment arm is closed. No study treatment crossover will be allowed. All patients should complete all visit procedures through Week 24, including patients who stop pacritinib treatment or have protocol-defined progressive disease prior to Week 24, unless patient withdraws consent, dies, undergoes splenic irradiation or splenectomy, or initiates any nonprotocol-directed anti-myelofibrosis treatment. Following regulatory, Ethics or Institution Review Board approval of Amendment 6, study treatment for patients at and beyond the week-24 timepoint will terminate. Study assessments will cease following the End-of-Treatment or 30-day post (EOT) visit, as applicable. Patients who are benefiting from therapy as of study treatment termination may be allowed to continue receiving pacritinib under single patient expanded access or named patient programs at the investigator's discretion and subject to regulatory and Ethics or IRB approval.

The dosage selection process will be based on efficacy and safety parameters, including model-based dose response as described in Section 3.1.

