3.3 Treatment Continuation After Progression of Disease

Patients who have progression of disease on MRI (preferred) or CT scan, defined as an increase in splenic volume of \geq 25% from baseline on MRI or CT scan, will not be allowed to continue study treatment. Patients should continue the visit schedule through Week 24 (including imaging and all protocol-specified study assessments) despite treatment discontinuation or disease progression prior to Week 24, unless patient withdraws consent, dies, undergoes splenic irradiation or splenectomy, or initiates any non-protocol-directed anti-myelofibrosis treatment.

4 Patient Selection and Withdrawal

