4.2 Criteria for Withdrawal of Patients

4.2.1 Withdrawal from Study Treatment and Procedures

Patients may discontinue or be withdrawn from treatment at any time. All reasonable efforts should be made to retain patients who discontinue treatment in the study and to conduct visits through Week 24 required by the protocol, including MRI (preferred) or CT scanning and follow-up for progressive disease, and leukemic transformation. Reasons for discontinuing treatment may include but are not limited to the following:

- Documented disease progression as defined in Section 3.2.
- Unrelated intercurrent illness that, in the judgment of the principal investigator, will affect assessments of clinical status to a significant degree
- Pregnancy
- Patient's decision
- Patient noncompliance with study drug
- Clinical need for concomitant therapy that is not permitted in the study
- Decision on the part of the investigator or CTI BioPharma Corp. medical monitor that it is in the patient's best interest to withdraw from study treatment
- Sponsor decision to terminate study
- Death

5 Method of Treatment Assignment and Blinding

Initially, eligible patients will be centrally randomized in a 1:1:1 allocation ratio to pacritinib 100 mg QD, pacritinib 100 mg BID, or pacritinib 200 mg BID using a central interactive web response system. If interim monitoring analysis indicates that any one of the treatment arm meets the stopping criteria (Section 11.9) for efficacy or safety and is thus dropped, then the randomization will be updated to a 1:1 ratio of the two remaining study arms. In the case of two arms being dropped by interim efficacy or safety monitoring, then all eligible patients will be enrolled to the remaining one active arm until up to 30 evaluable subjects are enrolled for that arm.

Randomization will be stratified by geographic region (North America, Europe, versus rest of the world [ROW]) and baseline platelet count (\leq 50,000/µL; >50,000/µL and \leq 100,000/µL; and >100,000/µL). The most recent platelet count obtained prior to start of treatment will be the basis of stratification by baseline platelet count.

A patient's treatment assignment will be known to all except the independent radiographic and cardiology assessors who will remain blinded to patient treatment assignment throughout the study.

6 Study Treatment

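### Table 6 takes a patient with grade 4 diarrhea at the 100 mg QD dose level out of the study, while the follow-up rule keeps patients who stop pacritinib in scheduled visits to Week 24 (internal inconsistency, low severity)

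*Protocol*

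**What the plan says.** The grade 4 row of Table 6 (protocol Section 6.5.4) treats the lowest dose level separately: "If grade 4 toxicity occurs at the lowest dosage of 100 mg QD, the patient will be discontinued from the study". At higher levels, if the event resolves in time, "treatment may be resumed, but dosage will be reduced by 1 dosage level from the level at which the toxicity was observed", and leaving the study is not mentioned. The grade 3 row of the same table ends only the drug: "If the toxicity recurs after restart at the lower dosage level, pacritinib treatment must be discontinued".

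The follow-up rule appears in several places:

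- Section 3 (and the Synopsis): "All patients should complete all visit procedures through Week 24, including patients who stop pacritinib treatment".
- Section 3.3 repeats it, names imaging expressly, and gives the exceptions: "unless patient withdraws consent, dies, undergoes splenic irradiation or splenectomy, or initiates any non-protocol-directed anti-myelofibrosis treatment".
- Section 4.2.1: "All reasonable efforts should be made to retain patients who discontinue treatment in the study and to conduct visits through Week 24".
- The Special Cases text after Table 1: "Patients who discontinue pacritinib treatment prior to Week 24, with or without disease progression, will continue to follow this Study Assessments Calendar through Week 24". The same text also ends visits, after an End of Treatment and a 30-day visit, when an arm is closed.

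SAP Section 7 tabulates leaving the study and stopping treatment separately, each with its own list of reasons. Adverse event is listed for stopping treatment but not for leaving the study.

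**The concern.** A patient with grade 4 diarrhea at 100 mg QD falls under two instructions that cannot both be followed. Table 6 ends participation. The follow-up rule continues visits to Week 24, and a toxicity event is none of its exceptions.

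The primary efficacy variable for dosage selection is percent spleen volume reduction at Weeks 12 and 24 (protocol Section 11.1, SAP Section 10). If Table 6 is applied as written, scans and symptom diaries after the event are missing because of toxicity, and the rule that removes them operates at one dose level. In a dose-finding trial, missingness that depends on both tolerability and dose is worth avoiding even when few patients are involved. This case comes from a single phrase.

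**Working it through.** The plan states no figure on this point to reproduce. The check is a comparison of texts, followed by a rough sizing.

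**1. Does the phrase mean participation or only treatment?** Three things favor the literal reading.

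- Section 3 times the dose decision for when all enrolled patients have reached Week 24 or have discontinued the study, so discontinuing the study is there the alternative to reaching Week 24.
- SAP Section 7 keeps the two kinds of discontinuation apart. An exit under Table 6 would have to be recorded under physician decision or other.
- The grade 3 row of Table 6, the grade 4 hemorrhage row of Table 3, and Table 4 name pacritinib or treatment as what stops.

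Two limits apply. The 100 mg QD entries in Table 3 use the bare verb with no object, so they settle nothing. The grade 4 row of Table 7 opens with the same clause, but its ending could not be read in the copy reviewed, so whether Table 6 is unique is not established.

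**2. Which scans are lost?** Inputs:

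- SAP spleen volume windows: days 63 to 105 (Week 12) and 147 to 189 (Week 24).
- An End of Treatment visit with spleen imaging is required within 7 days of stopping (Table 1 and its footnote 5; Section 7.1.1.1).
- The 30-day post-treatment visit has no spleen imaging.

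For a patient who leaves after the End of Treatment visit:

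- That scan falls on day 63 or later only if treatment stops on day 56 or later (56 + 7 = 63). Stopping before day 56 leaves no scan in either window. Stopping from day 56 to day 62 may or may not yield one.
- After the Week 12 scan, stopping before day 140 (140 + 7 = 147) leaves no Week 24 scan. The SAP carries Week 12 forward, but only as a supportive analysis (SAP Section 12.1).
- A patient with no in-window scan drops out of the mean percent reduction. The patient also counts as a non-responder in the ≥35% proportion, because its denominator is the whole FAS (SAP Section 10.1).

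**3. How many patients?** Inputs: up to 50 per arm (Section 11.7); grade 3/4 diarrhea of 3.8% at 200 mg BID in the pooled phase 3 studies (Section 1.3.4). Neither document gives a grade 4 rate, or any diarrhea rate at 100 mg QD, so 0.5% to 2% is an assumption. Expected number = 50p; chance of at least one = 1 − (1 − p)^50.

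| Rate p | Expected in 50 | Chance of at least one |
|---|---|---|
| 0.5% (assumed) | 0.25 | 22% |
| 1% (assumed) | 0.5 | 39% |
| 2% (assumed) | 1.0 | 64% |
| 3.8% (grades 3 and 4 together, four times the daily dose) | 1.9 | 86% |

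The last row serves as a ceiling. Patients who reach 100 mg QD by dose reduction are not counted.

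**4. What would it do to the estimates?** With the SD of 20% in Section 11.7, the 95% half-width for mean percent reduction is 1.96 × 20/√50 = 5.54 points with 50 patients and 1.96 × 20/√48 = 5.66 with 48. One would-be responder counted as a non-responder lowers the ≥35% proportion by 1/50 = 2 percentage points.

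**The case against.** The strongest reply is that this is one loose phrase set against a follow-up rule stated several times, and that most sites would follow the rule. The End of Treatment scan is still required and may fall in a window. SAP Section 12.1 also summarizes spleen volume at End of Treatment. At most about one patient in 50 is expected under the assumed rates, no hypothesis is tested, and precision barely moves. All of this stands, and it sets the severity. It does not remove the contradiction: if the sponsor meant study treatment, the phrase still says something else.

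A reader might infer more than the documents support:

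- *That the loss belongs to the 100 mg QD arm.* The trigger is the current dose level. Patients reduced from either BID arm can reach it, and efficacy is analyzed by randomized arm. The burden would fall more on the QD arm, which starts there, but not on it alone.
- *That everyone who stops is otherwise followed.* Besides the four listed exceptions, arm closure ends visits (Special Cases text; SAP Section 3). Section 4.2.1 asks for reasonable efforts, which is not a guarantee.
- *That Week 12 and Week 24 data are certain to be lost.* Only visits after the event are exposed, only if Table 6 is applied literally, and the End of Treatment scan may still count.
- *That early exit was a deliberate design choice.* Nothing in either document says so.

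**Conclusion.** The inconsistency is real and of low severity. For grade 4 diarrhea at the 100 mg QD dose level, Table 6 ends study participation, and the Week 24 follow-up rule does not allow for that. The consequence depends on sites applying Table 6 literally. A patient stopping before about day 63 could then have no in-window spleen scan and would count as a non-responder in the ≥35% proportion.

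The size rests on an assumed grade 4 rate of 0.5% to 2%, which gives 0.25 to 1 patient in 50. It would be tempting to call this a material threat to the dose comparison. The documents do not support that, since even two patients lost from 50 widen the half-width by only 0.12 points (5.66 − 5.54).

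**What to change.** Reconcile the grade 4 wording in Table 6 with Sections 3, 3.3 and 4.2.1 and the Special Cases text. It should state whether study participation or only study treatment ends, and it should agree with the Week 24 follow-up rule. Check the grade 4 row of Table 7 for the same wording and align it if needed.

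This asks only for clarity on follow-up. It changes no dose, hold, reduction or stopping rule. The cost is a phrase in one or two table cells at the next amendment. If only treatment ends, no visit is added that the calendar does not already schedule.

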6.6 Concomitant and Excluded Therapies

Ruxolitinib should not be administered concurrently with pacritinib at any time. Although there is no washout period required for ruxolitinib prior to the start of dosing with pacritinib, it should be understood that because of the difference in half-life between ruxolitinib (3 hours Jakafi package insert) and pacritinib (approximately 40 hours), there will be a period of 10 to 14 days following the discontinuation of ruxolitinib and the start of dosing with pacritinib, during which pacritinib has not yet reached steady state and during which patients may be at increased risk of ruxolitinib withdrawal, particularly after high doses of ruxolitinib (eg, more than 10 mg BID or 20 mg QD). For this reason, patients who are on more than 10 mg BID (or 20 mg QD) of ruxolitinib at the time of consent for this study must taper the ruxolitinib dose down to 10 mg BID or lower and remain stable on the reduced dose for at least 2 weeks prior to starting pacritinib. Tapering should be done per institutional practice and may be done with concurrent addition of prednisone during the screening period. In addition to any steroids used during the screening period, the protocol permits short-term use (up to 14 days) of corticosteroids and/or hydroxyurea as prophylaxis or treatment of symptomatic ruxolitinib withdrawal during the first month of treatment with pacritinib.

Supportive care therapies, except when prohibited by any of the below provisions, are permitted, including the use of low-dose aspirin. Corticosteroids (up to 20 mg/day of prednisone or equivalent) and/or hydroxyurea may be used for up to 2 weeks during the first month of treatment with pacritinib to control symptoms of ruxolitinib withdrawal if they occur. Treatments for MF that might be considered supportive care are only allowable with medical monitor approval prior to administration.

The following therapies and procedures are prohibited throughout the study:

- Chemotherapy, interferon, or other treatment for MF, with the exception of up to 2 weeks of corticosteroids (up to 20 mg/day prednisone or equivalent) and/or 2 weeks of hydroxyurea as needed to reduce the risk of or treat the symptoms of ruxolitinib withdrawal
- Antiplatelet or anticoagulation agents, with the exception of $\leq 100 \text{ mg/day}$ of aspirin
- Growth factor therapies, including erythropoietin and thrombopoietin
- Strong CYP3A4 inhibitors (Appendix 5) and strong CYP450 inducers (Appendix 6), except as needed to treat AEs, with medical monitor approval
- Any drugs with significant potential for QTc prolongation (Appendix 8), except as needed to treat AEs, with medical monitor approval
- Splenic irradiation or splenectomy

Also refer to the Pacritinib Dosage Management Guidelines (Section 6.5) for guidelines on treatment of AEs.

6.6.1 Management of Gastrointestinal Toxicity

The need for managing gastrointestinal (GI) effects of pacritinib, particularly diarrhea, should be anticipated. A careful baseline evaluation of bowel habits (frequency and consistency of bowel movements) should be obtained at baseline for all patients.

At the baseline visit, all patients will be provided with a prescription (and instructions to fill that prescription) for loperamide (Imodium[®]) or a similarly effective antidiarrheal drug. Patients will be instructed to start taking the prescribed loperamide or other antidiarrheal drug per package and physician instructions as soon as they notice any changes in frequency or consistency of bowel movements after starting study treatment.

Early intervention for diarrhea should be initiated for patients with increases of one grade or more in diarrhea (Appendix 9). At the investigator's discretion, prophylactic use of antidiarrheals may be initiated for patients or populations in whom it is judged necessary to enhance patient safety. Standard supportive care measures to control symptoms of GI toxicity such as diarrhea, constipation, and nausea should be provided.

7 Study Assessments

7.1 Criteria for Evaluation

7.1.1 Efficacy

Efficacy assessments will be performed as described below until approval of Amendment 6, at which point assessments cease following the patient's End-of-Treatment, or 30-day post (EOT) visit as applicable.

7.1.1.1 Spleen Volume

MRI is the preferred modality; CT scan will be used for patients who cannot undergo MRI, or for whom MRI is not available. Imaging should be performed without contrast agent. For each patient, the same imaging modality should be used throughout the study.

Spleen volume will be measured by MRI (preferred) or CT at screening and at the end of weeks 12 and 24 visits. Spleen volume will also be measured at the end of treatment if this does not occur at the end of

Week 24. For patients who continue on pacritinib past Week 24, spleen volume will be assessed by MRI or CT every 3 months up to 2 years. Patients who discontinue treatment (except withdraw of consent or death) will be required to complete the end of treatment visit within 7 days of stopping treatment. Unscheduled imaging studies may be performed at physician discretion if he/she considers disease-related symptoms to be worsening. All images generated as part of unscheduled evaluations must be submitted by the investigator for central review. An independent radiologist, blinded to all patient and site identifiers and treatment assignments, will measure spleen volume. While images generated as part of unscheduled visits may be read locally if treatment discontinuation is being considered, only the scheduled centrally read images will be used for the efficacy analysis.

